## **5.2 Secondary objectives and endpoints**

*Secondary objective 1:*

To further evaluate the humoral and cellular systemic immune responses to the different vaccine regimens

*Secondary endpoint 1:*

Occurrence and level of vaccine-induced serum IgG Ab binding to the 3 gp120 Env proteins contained in the vaccine regimen (ZM96, TV1.C, and 1086.C) at the Month 12, 12.5, and 18 timepoints

Vaccine-induced serum IgG Ab binding to V2 Env proteins at 6.5, 12, 12.5, and 18 months

Vaccine-induced CD4+ T-cell responses to the HIV proteins included in the vaccine at 6.5, 12, 12.5, and 18 months

Vaccine-induced serum IgG3 Ab binding to Env proteins at 6.5, 12, 12.5, and 18 months

HIV-specific CD4+ T cell polyfunctionality by ICS

*Secondary objective 2:*

To evaluate the safety and tolerability of each vaccine regimen through Month 18

*Secondary endpoint 2:*

Endpoints as indicated in primary endpoints 2

## **5.3 Exploratory objectives**

*Exploratory objective 1*

To conduct analyses related to furthering the understanding of HIV, immunology, vaccines, and clinical trial conduct

*Exploratory endpoint 1*

Additional immunogenicity assays may be performed on blood and mucosal samples, including samples at innate and adaptive immunity timepoints, based on the HVTN

Laboratory Assay Algorithm. These assays are outlined in the Laboratory Accessory document.

*Exploratory objective 2*

To assess whether the gut microbiome correlates with vaccine responses

*Exploratory endpoint 2*

Gut microbiome characterization via rRNA sequencing using optionally provided stool specimens

#### 6.1.1 Sample size calculations for safety

The goal of the safety evaluation for this study is to identify safety concerns associated with product administration. The ability of the study to detect serious adverse events (SAEs) (see Section 11.2.3) can be expressed by the true event rate above which at least 1 SAE would likely be observed and the true event rate below which no events would likely be observed. Specifically, for each adjuvanted vaccine arm of the study ( $n = 36$ ), there is a 90% chance of observing at least 1 event if the true rate of such an event is 6.2% or more; and there is a 90% chance of observing no events if the true rate is 0.3% or less. For the unadjuvanted vaccine arm ( $n = 24$ ), there is a 90% chance of observing at least 1 event if the true rate of such an event is 9.1% or more; and there is a 90% chance of observing no events if the true rate is 0.4% or less. For the vaccine arms combined ( $n = 132$ ), there is a 90% chance of observing at least 1 event if the true rate of such an event is 1.7% or more; and there is a 90% chance of observing no events if the true rate is

0.08% or less. As a reference, in HVTN vaccine trials from December 2000 through April 2014, about 6.5% of South African participants who received placebos experienced an SAE.

Probabilities of observing 0, 1 or more, and 2 or more events among arms of size 24 and 36 are presented in Table 6-1 for a range of possible true adverse event rates. These calculations provide a more complete picture of the sensitivity of this study design to identify potential safety problems with the vaccine.

**Table 6-1 Probability of observing 0 events, 1 or more events, and 2 or more events, among vaccine arms of size 24 and 36, for different true event rates**

True event rate (%)	Pr(0/24)	Pr(1+/24)	Pr(2+/24)	Pr(0/36)	Pr(1+/36)	Pr(2+/36)
0.1	0.976	0.024	<0.001	0.965	0.035	0.001
0.5	0.887	0.113	0.006	0.835	0.165	0.014
1	0.786	0.214	0.024	0.696	0.304	0.050
4	0.375	0.625	0.110	0.230	0.770	0.425
10	0.080	0.920	0.708	0.023	0.977	0.887

An alternative way of describing the statistical properties of the study design is in terms of the 95% CI for the true rate of an adverse event based on the observed data. Table 6-2 shows the 2-sided 95% CIs for the probability of an event based on a particular observed rate. Calculations are done using the score test method [70]. If none of the 132 participants receiving a vaccine regimen experience a safety event, the 95% 2-sided upper confidence bound for the true rate of such events in the total adjuvant-vaccinated population is 2.8. For each individual adjuvanted vaccine arm ( $n = 36$ ), the 2-sided upper confidence bound for this rate is 9.6%. For the vaccine arm with no adjuvant ( $n = 24$ ), the 2-sided upper confidence bound for this rate is 13.8%.

**Table 6-2 Two-sided 95% CIs based on observing a particular rate of safety endpoints for vaccine arms of size 24, 36, and 132 (pooled)**

Observed event rate	CI (%)
0/24	(0.0, 13.8)
1/24	(0.2, 20.2)
2/24	(2.3, 25.8)
0/36	(0.0, 9.6)
1/36	(0.5, 14.2)
2/36	(1.5, 18.1)
0/132	(0.0, 2.8)
1/132	(0.0, 4.2)
2/132	(0.4, 5.4)

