#### 6.4.3.2 AEs and SAEs

AEs will be summarized using MedDRA System Organ Class and preferred terms. Tables will show by treatment arm the number and percentage of participants experiencing an AE within a System Organ Class or within preferred term category by severity or by relationship to study product. For the calculations in these tables, a participant with multiple AEs within a category will be counted once under the maximum severity or the strongest recorded causal relationship to study product. Formal statistical testing comparing arms is not planned since interpretation of differences must rely heavily upon clinical judgment.

A listing of SAEs reported to the DAIDS Regulatory Support Center (RSC) Safety Office will provide details of the events including severity, relationship to study product, time between onset and last vaccination, and number of vaccinations received.

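### Section 6.1.1 safety figures: one wrong probability in Table 6-1, a zero-event bound given to the wrong population, and one-event limits in Table 6-2 that follow no single method

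*Combined protocol and SAP*

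**What the plan says.** Section 6.1.1 describes safety sensitivity for the 24-person unadjuvanted arm, for each of the three 36-person adjuvanted arms, and for all 132 participants together.

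- **Table 6-1** lists the probability of 0, of 1 or more, and of 2 or more events for n = 24 and then n = 36. The row for a 4% true rate is "4 0.375 0.625 0.110 0.230 0.770 0.425".
- **The text above Table 6-2** names the interval method: "Calculations are done using the score test method [70", citing reference 70. It begins its zero-event statement with "If none of the 132 participants receiving a vaccine regimen experience a safety event" and concludes that the "95% 2-sided upper confidence bound for the true rate of such events in the total adjuvant-vaccinated population is 2.8", with no percent sign.
- **Table 6-2** gives these intervals (%) for a single event: 1/24 (0.2, 20.2); 1/36 (0.5, 14.2); 1/132 (0.0, 4.2).

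Section 6.4.3.2 says of adverse events: "Formal statistical testing comparing arms is not planned since interpretation of differences must rely heavily upon clinical judgment".

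**The concern.** Safety is a primary objective and the plan has no between-arm tests of adverse events. The probabilities and intervals in Section 6.1.1 are therefore a main quantitative statement of what each arm can reveal about them.

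The 0.110 looks wrong beside its neighbours. With 1 or more events at 0.625, it implies a probability of exactly one event of 0.625 − 0.110 = 0.515, which is implausibly high for 24 participants. If it is wrong, the table misstates how well the smallest arm can show a repeated event and exaggerates its disadvantage against the 36-person arms.

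The zero-event sentence starts from all 132 participants and ends with a population that excludes the 24 unadjuvanted ones. In Table 6-2 the lower limit for one event is smaller at n = 24 than at n = 36, although one event in fewer people is a higher observed rate.

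**Working it through.** **Inputs.** From Section 6.1.1 and Table 3-1: n = 24 (unadjuvanted), n = 36 (each adjuvanted arm) and n = 132 (all). The adjuvanted total is 3 × 36 = 108. Intervals are two-sided 95%, so z = 1.96 and z² = 3.84.

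**1. Table 6-1, n = 24, rate 4%** (binomial)

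- Pr(0) = 0.96^24 = 0.3754; printed 0.375.
- Pr(1 or more) = 1 − 0.3754 = 0.6246; printed 0.625.
- Pr(exactly 1) = 24 × 0.04 × 0.96^23 = 0.3754.
- Pr(2 or more) = 1 − 0.3754 − 0.3754 = **0.2492**; printed **0.110**.

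The n = 36 cells in the same row reproduce (0.2300, 0.7700, 0.4250), as do the other four rows, to about 0.001. Only this one of 30 cells fails.

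The printed row is also impossible on its own terms. Pr(exactly 1 of 24) is largest at a rate of 1/24, where it equals (23/24)^23 = 0.376. No event rate gives the implied 0.515. A value of 0.110 for two or more events in 24 corresponds to a true rate of about 2.4% (2.3% gives 0.105 and 2.4% gives 0.112).

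- Shortfall: (0.249 − 0.110)/0.249 = 56%.
- Chance of 2 or more events, 36-person arm relative to 24-person arm: 0.425/0.110 = 3.9 as printed; 0.425/0.249 = 1.7 when correct.

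**2. Zero-event upper bound** (score method, z²/(n + z²))

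- n = 132: 3.84/135.84 = 2.83%, which reproduces the printed 2.8.
- n = 108: 3.84/111.84 = 3.43%.

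The number belongs to all 132 participants; the label names the 108.

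**3. Table 6-2, one event**

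The plain score (Wilson) limits, with p = x/n, are [p + z²/2n ± z√(p(1−p)/n + z²/4n²)]/(1 + z²/n). For 1/24 the lower limit is (0.1217 − 0.1131)/1.1601 = 0.0074, or 0.74%. The modified lower limit for x = 1 is −ln(0.95)/n.

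| Observed | Printed (%) | Plain score (%) | Modified lower limit (%) |
|---|---|---|---|
| 1/24 | 0.2, 20.2 | 0.74, 20.24 | 0.21 |
| 1/36 | 0.5, 14.2 | 0.49, 14.17 | 0.14 |
| 1/132 | 0.0, 4.2 | 0.13, 4.17 | 0.04 |

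The plain score method reproduces all the upper limits and every zero-event and two-event row. Of the one-event lower limits it matches only 1/36; the modified limit matches 1/24 and 1/132 but not 1/36. The continuity-corrected score, Agresti–Coull, Clopper–Pearson, Jeffreys, Wald, mid-P and likelihood-ratio intervals were also tried, and none gives the three printed lower limits together. Under both the plain and the modified limit, the value falls as n rises from 24 to 36; the printed value rises from 0.2 to 0.5.

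**Figures that hold.** The 90% detection thresholds in the text (6.2%/0.3%, 9.1%/0.4%, 1.7%/0.08%) and all of Table 6-3 reproduce.

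**The case against.** The strongest reply is that nothing depends on these figures. The pause and review triggers in Table 11-1 act on single events, and the Safety Monitoring Board reviews in Section 11.1.2 set no two-event threshold. The headline detection thresholds in Section 6.1.1 are correct, as are all the upper limits in Table 6-2. The wrong cell understates sensitivity, so it reassures nobody falsely. The denominator of the 2.8 bound can be recovered from the same sentence and from the pooled row of Table 6-2. The disputed lower limits differ by about half a percentage point at most.

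All of that stands, and it limits the importance of the point. It does not make the printed figures right. The population label also errs in the other direction from the table cell: it gives adjuvanted recipients a tighter bound (2.8%) than 108 participants support (3.4%).

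A second objection is that the documents do not show which one-event convention was meant. If the modified limit is part of the cited method or of the software, 1/24 and 1/132 are right and only 1/36 is wrong. That also stands. Table 6-3 reproduces with the plain score interval, but its smallest count is 6, so it cannot settle the one-event case. What is established is that the three limits are mutually inconsistent under either convention.

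**Conclusion.** The concern holds in all three parts.

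- The Table 6-1 cell is wrong: 0.249, not 0.110. This assumes only independent events at a common rate, the model that reproduces the rest of the table.
- The 2.8% bound is numerically right for 132 and wrongly labelled; the adjuvanted-only figure is 3.4%. The percent sign is missing.
- The one-event lower limits in Table 6-2 do not come from one method. Under the plain score method 1/24 and 1/132 are wrong; under the modified limit 1/36 is wrong.

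The first item matters most, because it understates by more than half the unadjuvanted arm's chance of showing a repeated event at a 4% rate. The consequence is confined to how readers judge the safety sensitivity of the design. Sample size, tests and decision rules are unaffected.

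**What to change.** 1. In Table 6-1, change Pr(2+/24) at a 4% rate from 0.110 to 0.249.
2. In the text above Table 6-2, delete the prefix *adjuvant-* and print 2.8%. If the adjuvanted arms alone are meant, state 0/108 and give 3.4%.
3. In Table 6-2, apply one method to the three one-event rows and say which. The plain score method gives lower limits of 0.7, 0.5 and 0.1; the modified limit, if intended, should be stated and gives 0.2, 0.1 and 0.0. The upper limits stay as they are.

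The cost is editorial: one cell, one phrase and one or two lower limits, with no effect on trial conduct or analysis.

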### 6.1.2 Sample size calculations for immunogenicity

The primary immunogenicity objective of this trial is to characterize the vaccine-induced humoral immune responses of the 4 vaccine regimens at Month 6.5. The precision with which the true response rate can be estimated from the observed data depends on the true underlying response rate and the sample size. Two-sided 95% CIs for the response rate based on observing a particular rate of responses in the vaccinees is shown in Table 6-3.

Calculations are done using the score test method [70]. The sample size  $n = 20$  and  $n = 30$  assume a 15% missing data rate.

Another primary question of interest regarding immunogenicity is the comparison of the Month 6.5 response rates of insert-directed serum IgG from the binding Ab assay to detect moderate differences in response rates between the 2 arms primed with ALVAC followed by ALVAC + Bivalent Subtype C gp120 adjuvanted either with MF59® or with alum. A separate primary objective is to compare the Month 6.5 response rates of insert-directed serum IgA from the binding Ab assay for the arm primed with ALVAC followed by ALVAC + Bivalent Subtype C gp120 adjuvanted with MF59® to the arm with concurrent administration of ALVAC and Bivalent Subtype C gp120 adjuvanted with MF59® at all vaccination timepoints. Within each of these group comparisons, no adjustment will be made for the use of multiple inserts.

**Table 6-3 Two-sided 95% CIs for the true response rate based on observing a particular rate of responses in the vaccinees ( $n = 20, 30$ )**

n	No. of responses	Observed response rate (%)	CI (%)
20	6	30.0	(14.5, 51.9)
20	10	50.0	(29.9, 70.1)
20	12	60.0	(38.7, 78.1)
20	14	70.0	(48.1, 85.5)
20	16	80.0	(58.4, 91.9)
30	9	30.0	(16.7, 47.9)
30	15	50.0	(33.2, 66.8)
30	18	60.0	(42.3, 75.4)
30	21	70.0	(52.1, 83.3)
30	24	80.0	(62.7, 90.5)

As shown in Table 6-4, there is adequate power for a formal comparison of immunogenicity response rates between adjuvanted vaccine arms of size  $n = 30$  to detect moderate differences in response rates of ~35%. These calculations use a Fisher's exact 2-sided test with a Type I error rate of 0.05.

**Table 6-4 Power for comparison of response rates between 2 arms ( $n_1 = 30, n_2 = 30$ )**

True response rate Arm 1 (%)	Maximum true response rate in Arm 2 in order to detect a difference	
	80% power	90% power
40	8	5
50	14	10
60	22	18
70	32	27
80	42	37
90	56	51
95	64	59

In addition to comparing insert-directed serum IgG response rates at Month 6.5 between the aluminum hydroxide and MF59® adjuvanted arms, it is also of interest to compare

differences in the magnitudes of the responses. Power calculations use Lachenbruch's 2-part test to compare the response rates and the continuous insert-directed IgG responses at Month 6.5. Given that power is sufficient to compare the response rates, the study will also be well powered for this comparison involving magnitudes. For example, with  $n = 30$  per arm there is 80% power to detect a difference with a true response rate of 92% in 1 arm with  $GM = 6.31$  and variance of 2.06 in responders and a response rate of 80% in the other arm with  $GM = 5.18$  and variance of 2.06 in responders. Response rates of 92% and 94% with  $GMs$  of 6.31 and 6.42 (variance 2.06, 1.89 respectively) correspond to the responses observed at Month 6.5 in RV144 with the A244 and 92TH023 inserts. See Table 6-5 for power with other response rates and magnitudes (variance = 2.06 for each arm for true response rate = 92% and variance = 1.89 for true response rate = 94%)

Many other immunogenicity endpoints will also be analyzed to characterize the innate and adaptive immune profiles of the vaccine arms. These include vaccine-induced IgG Ab binding to V2 Env proteins, vaccine-induced CD4+ T-cell responses to the HIV proteins included in the vaccine and vaccine-induced IgG3 Ab binding to Env proteins.

**Table 6-5 Power for comparison of response rates and levels between 2 vaccine arms ( $n1 = 30$ ,  $n2 = 30$ )**

True response rate (%) and GM Arm 1	Maximum true response rate and GM in Arm 2 in order to detect a difference			
	80% power		90% power	
94	6.42	85	5.25	85
94	6.42	80	5.37	80
94	6.42	75	5.51	75
92	6.31	85	5.15	85
92	6.31	80	5.18	80
92	6.31	75	5.22	75

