For quantitative assay data (eg, level of vaccine-induced IgG Ab binding to the 2 gp120 Env proteins contained in the vaccine regimen), graphical and tabular summaries of the distributions by antigen, treatment arm, and timepoint will be made. The difference between arms at a specific timepoint will be tested with a nonparametric Wilcoxon rank sum test if the data are not normally distributed and with a 2-sample t-test if the data appear to be normally distributed. To test for differences among the 4 vaccine arms, first a Kruskal-Wallis rank test or an F-test (depending on the normality assumption) will be used to test for overall differences. Secondly, if the overall test is significant at the 2-sided 0.05 level, then individual tests comparing the 3 pairs of vaccine arms will be done unless pre-specified. If rank-based tests are used then the tests will be inverted to construct Hodges-Lehmann point-estimates and 2-sided  $(1 - 0.05/3) \times 100\%$  CIs about the differences in location centers of the 3 pair-wise comparisons of vaccine arms. An appropriate data transformation (eg,  $\log_{10}$  transformation) may be applied to better satisfy assumptions of symmetry and homoscedasticity (constant variance).

Some immunologic assays have underlying continuous or count-type readout that are dichotomized into responder/nonresponder categories (eg, binding antibody multiplex assay [BAMA]). If treatment arm differences for these assays are best summarized by a mixture model, then Lachenbruch's test statistic [71] will be used to evaluate the composite null hypothesis of equal response rates in the MF59® vs aluminum hydroxide adjuvanted arms and equal response distributions among responders in the 2 arms. This test statistic equals the square of a binomial Z-statistic for comparing the response rates plus the square of a Wilcoxon statistic for comparing the response distributions in the subgroup of responders. A permutation procedure is used to obtain a 2-sided p-value. For estimation, differences in response rates between arms will be estimated using the methods described above, and in the subgroup of positive responders, differences in location parameters between arms will be estimated using the methods described above.

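### Table 6-5: the entry 92%/GM 6.31 versus 85%/GM 5.15 is listed under 80% power, but the plan's own two-part test gives about 75%

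*Combined protocol and SAP*

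**What the plan says.** Section 6.1.2 first gives power for response rates alone (Table 6-4), using a "Fisher's exact 2-sided test with a Type I error rate of 0.05". It then turns to response magnitudes: "Power calculations use Lachenbruch's 2-part test to compare the response rates and the continuous insert-directed IgG responses at Month 6.5". The arms are of size 30, the figure that Section 6.1.2 uses for arms of 36 when it says that the sizes "assume a 15% missing data rate". The variance among responders is given as "variance = 2.06 for each arm for true response rate = 92" percent, and as 1.89 where the true response rate is 94%.

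Table 6-5 ("Power for comparison of response rates and levels between 2 vaccine arms") lists, under 80% power, Arm 1 at 92% with GM 6.31 against Arm 2 at 85% with GM 5.15. A worked example in the text covers the neighbouring row, 92%/6.31 against 80%/5.18: "there is 80% power to detect a difference with a true response rate of 92% in 1 arm".

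Section 6.4.4.1 defines the test: "This test statistic equals the square of a binomial Z-statistic for comparing the response rates plus the square of a Wilcoxon statistic" for the responders. On the p-value it says: "A permutation procedure is used to obtain a 2-sided p-value".

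**The concern.** Table 6-5 is the only stated power for the level half of primary endpoint 1 (Section 5.1 covers both occurrence and level of binding IgG), and Section 6.1.2 concludes from it that the magnitude comparison is well powered. An entry under 80% should therefore have 80% power with the test the plan defines.

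The table itself gives a reason to check. As the Arm 2 response rate falls from 85% to 80% to 75%, the response-rate part contributes more, so the GM part can contribute less. In the 94% rows the Arm 2 GM accordingly rises from 5.25 to 5.37 to 5.51, by 0.26 in all. In the 92% rows it rises only from 5.15 to 5.18 to 5.22, by 0.07. Both sets can hardly be at constant power.

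**Working it through.** **Inputs.** Test and statistic: Sections 6.1.2 and 6.4.4.1. n = 30 per arm, response rates and GMs: Table 6-5. Variance 2.06 (92% rows) and 1.89 (94% rows): Section 6.1.2. Assumed: alpha 0.05, as for Table 6-4, and normal responder values with the GM taken as the mean on the scale of the variance.

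**Hand check of the disputed cell.**

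- Response rates: pooled rate (0.92 + 0.85)/2 = 0.885. Z = 0.07/√(0.885 × 0.115 × 2/30) = 0.07/0.0824 = 0.85, so Z² = 0.72.
- Levels: expected responders 30 × 0.92 = 27.6 and 30 × 0.85 = 25.5. The chance that an Arm 1 responder exceeds an Arm 2 responder is Φ((6.31 − 5.15)/√(2 × 2.06)) = Φ(0.571) = 0.716. Wilcoxon Z = (0.716 − 0.5)/√(54.1/(12 × 27.6 × 25.5)) = 0.2162/0.0800 = 2.70, so its square is 7.30.
- Sum (non-centrality): 0.72 + 7.30 = 8.02.

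The same formulas for the other rows give 9.37, 9.04 and 8.91 (94% against 85, 80, 75) and 8.53 and 9.24 (92% against 80, 75). This approximation runs 2 to 3 points below simulation, so I use it only to rank the rows. The disputed cell is clearly the lowest. With an Arm 2 GM of 5.07 the sum becomes 8.94, in line with the rows that simulate at about 80%.

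**Simulation, all six 80% rows.** Responders are Binomial(30, p) and the statistic is as in Section 6.4.4.1. It is referred to chi-square with 2 df (30,000 to 40,000 trials) and, separately, to a permutation distribution (6,000 to 12,000 trials). The last column reads GM and variance literally: lognormal values with the variance on the raw scale.

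| Arm 1 | Arm 2 | Stated | Chi-square | Permutation | Lognormal |
|---|---|---|---|---|---|
| 94 / 6.42 | 85 / 5.25 | 80% | 82% | 83% | 84% |
| 94 / 6.42 | 80 / 5.37 | 80% | 80% | 81% | 82% |
| 94 / 6.42 | 75 / 5.51 | 80% | 79% | 79% | 81% |
| 92 / 6.31 | 85 / 5.15 | 80% | 75% | 75% | 77–78% |
| 92 / 6.31 | 80 / 5.18 | 80% | 77% | 77–78% | 79–80% |
| 92 / 6.31 | 75 / 5.22 | 80% | 81% | 81% | 82% |

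On the normal reading four of the six rows come out at 79 to 83%, close to the stated figure. Repeated runs of the disputed cell gave 74 to 75%. The simulation error is √(0.75 × 0.25/12,000) = 0.4 points or less.

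**Why the scale matters a little.** For a lognormal with geometric mean G and raw variance V, the log variance is ln[(1 + √(1 + 4V/G²))/2]. With V = 2.06 this is 0.0481 at G = 6.31 and 0.0699 at G = 5.15. The log difference is ln(6.31/5.15) = 0.203, so the exceedance probability is Φ(0.203/√0.118) = Φ(0.591) = 0.723 instead of 0.716. Hence 77 to 78% instead of 75%.

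**GM that gives 80%.** On the normal reading, at 92% against 85%, an Arm 2 GM of 5.07 gives 79.5 to 80.5%. The detectable difference is then 6.31 − 5.07 = 1.24 instead of 6.31 − 5.15 = 1.16.

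**The case against.** Section 6.1.2 names Lachenbruch's test for the power calculation but does not say which second part, p-value method, alpha, distribution or scale was used. The Wilcoxon and permutation details come from the analysis section. With a t statistic as the second part the disputed cell reaches 78 to 79%, and the lognormal reading gives 77 to 78%. A coarse simulation search by the sponsor could add a point or so: with 1,000 trials (an assumed number) the standard error is √(0.8 × 0.2/1,000) = 1.3 points. The consequence is also slight. Section 6.4.4.1 names Fisher's exact test on response rates as the primary comparison and brings in the two-part test only if a mixture model summarises the difference best.

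Much of this stands: it limits the size and severity of the point. It does not restore the cell. The t version takes other rows up to 82 to 86%, Section 6.4.4.1 specifies a Wilcoxon statistic, and no variant tried puts all six rows at 80%.

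A reader might infer more, and the documents do not support it:

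- *The worked example is wrong too.* For 92%/6.31 against 80%/5.18, power is 77 to 78% on the normal reading but 79 to 80% on the lognormal one. That is too close to call an error.
- *The 94% rows' variance was used by mistake.* Variance 1.89 lifts the disputed cell to 78–79%, but it also takes the 92% against 75% row to about 83%. Nothing in the text points to such a slip.
- *The affected row is the one nearest the expected data.* Section 6.1.2 gives no expected response rate for the alum arm.
- *The 90% column is wrong.* Its GM values are not legible in the text available to me, so there is no evidence either way.

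**Conclusion.** The concern holds for one cell. With the test of Section 6.4.4.1, 30 per arm and variance 2.06, the 92%/6.31 against 85%/5.15 entry has about 75% power, 5 points below its label. This rests on alpha 0.05 and on normal responder values with GM and variance on one scale. On the literal lognormal reading the shortfall is 2 to 3 points. The cell misses 80% on either reading, and only the size of the gap depends on what the plan leaves unstated. It would be wrong to infer that the trial as a whole is underpowered for levels, since the other rows lie at about 77 to 83% on the normal reading. Severity is low.

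**What to change.** In Table 6-5, either restate the 92%/6.31 against 85%/5.15 cell as about 75% power, or change its Arm 2 GM from 5.15 to about 5.07. The value 5.07 is for the normal reading; if another distribution was meant, recompute it. State under the table the alpha, the scale of the GM and variance, and the distribution assumed for responders. Recheck the worked example (92%/6.31 against 80%/5.18) in the same run and change it only if that run shows a shortfall.

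The cost is one table entry and a footnote. Sample size, randomisation and analysis stay as they are.
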